### **28.0** APPENDIX B: QMODE

#### Introduction QMODE Temperature Control Mode

The QDOT MICROTM catheter with QMODE introduces temperature controlled ablation to irrigated catheters. Temperature controlled ablation allows RF power to be delivered safely without tip char or steam pops. The QMODE temperature control mode utilizes the temperature sensing capabilities of the QDOT MICROTM catheter to optimize power delivery ensuring efficient ablation. When using the QMODE temperature control mode the irrigation rate will vary based on temperature to both cool the catheter tip adequately and retain temperature sensitivity, ensuring the safety profile.

The QMODE temperature control is designed to maximize RF lesion efficiency by using temperature feedback from the tip to adjust power and irrigation flow. The QMODE temperature control mode monitors the temperature rate of change in relationship to the set target temperature during RF application. To maintain a desired power levels at a safe temperature, the algorithm applies an accurate correction to control the irrigation flow rate.

- For maximum power settings, 35W or lower: The flow rate starts at low flow (4ml, lowest setting) to increase temperature sensitivity. If the set power is titrated down because the temperature exceeds the set target temperature (50°C), the generator changes the pump flow rate from low (4mL) to high flow (15 mL) to maintain the set maximum power. Once the temperature decreases the pump irrigation flow rate is returned to low (4mL).
- For maximum power settings, greater than 35W: The flow rate starts at high flow (15ml) for safety. If the temperature drops below the set maximum low flow temperature (45°C), the generator changes the pump from high (15 mL) to low (4mL) flow. The change to low flow allows the temperature to rise above the set maximum low flow temperature and closer to the target temperature.

#### 28.1 Use of the QDOT MICRO™ QMODE algorithm

In the event of spontaneous or induced AF and/or atrial flutter, the placement of additional RF lesions outside of the PV ostia in Qmode is at the discretion of the investigator and includes the following:

- Linear lesions between both superior PVs (roof line), the mitral annulus and the left inferior PV (mitral isthmus line) or between the LA roof and mitral annulus (anterior line)
- Ablation for any non-PV foci in the LA and/or RA, including isolation of the superior vena cava (SVC)
- Linear lesions in the cavo-tricuspid isthmus

If linear lesions are placed, it is recommended that complete conduction block across the ablation line be demonstrated by mapping and/or pacing maneuvers.

	Biosense Webster, Inc	
Version 5.0 – Feb 3, 2021	CONFIDENTIAL	Page 120 of 135

### 28.2 **Recommended ablation parameters**

QMODE temperature control mode will be used for PVI once the investigator deems QMODE+ unable to complete PVI. Additionally, QMODE temperature control mode will be used for all RF applications outside the PV ostia during the study ablation procedure (refer to Sections 13.3.4 and 13.3.5).

The QDOT MICROTM catheter with QMODE temperature control mode is designed to maximize RF lesion efficiency by using temperature feedback from the tip to adjust power and irrigation flow. For power levels from 1-50W, the generator changes the pump irrigation flow rate from low (4 mL/min) to high flow (15 mL/min) or from high to low flow to reach and maintain the set maximum power without exceeding the set target temperature (50°C). The QMODE temperature control mode minimizes the irrigation rate thus increasing temperature sensitivity at the catheter tip.

	Target Temp*		Cut-off Tem	р	Nominal	
Power	Range	Recommended	Range	Recommended	Irrigation Flow rate	
25-35 W	45-50°С	50°C	50-55°C	55°C	4mL**	
36-50W***	45-50°С	50°C	50-55°C	55°C	15mL**	

#### Table 28.2A: QMODE Ablation parameters

\* Temperatures displayed on the RF generator do not represent tissue temperature or electrode tissue interface temperature.

\*\* A minimum flow rate of 2mL during mapping is recommended.

\*\*\* RF applications at 36-50W should not exceed 30 sec.

**Note:** The default parameters for QMODE temperature control are user-adjustable, in case the investigator deems appropriate.

### **Recommendation for CoolFlow® Irrigation Pump Setting and RF Power-delivery**

The CoolFlow® Irrigation Pump will deliver a continuous infusion of 2 ml/min of room temperature heparinized saline (1 u heparin/1 ml saline) when not delivering RF energy. Increase the irrigation to high flow rate starting up to minimal 2 seconds before the onset of RF energy delivery and maintaining this higher flow rate up to 5 seconds after termination of the energy application.

### **QMODE** Contact Force (CF) Settings

When using the study catheter in QMODE the recommended Contact Force working range should be between 5 and 30g.

### Visitag Settings (recommendation)

It is recommended that ACCURESPTM be enabled; Respiratory Gating Mandatory (unless using Jet Ventilation)

	Biosense Webster, Inc	
Version 5.0 – Feb 3, 2021	CONFIDENTIAL	Page 121 of 135

- Stability Settings:
  - Range: 3 mm
  - Time: 3 seconds
- Filter (FOT) Settings:
  - $\circ~$  If an FOT filter is desired, the percentage of time of the chosen gram force is recommended to be set on 50%

# **Recommended Temperature Range and RF Power Settings**

- QMODE Temperature settings
  - Below or equal to 35 W
    - Temperature Cut-Off: 55°C
    - Target Temperature: 50°C
  - Above 35W
    - Temperature Cut-Off: 55°C
    - Target Temperature: 50°C (prevents overheating)

Note: The default parameters are user-adjustable, in case the investigator deems appropriate.

### **QMODE** Ablation Workflow:

- If the temperature increases rapidly, stop RF application immediately
- RF power range of 15-50 Watts (W) is recommended for atrial ablation
- At anatomical locations, not on the LA posterior wall or CS:
  - Maximum allowed power should not exceed 50 W
  - Duration of ablation should not exceed 60 seconds of continuous ablation at a given location
- Move/drag the catheter to a new location when clinically effective ablation is achieved (EGM reduction and/or impedance drop).
- Duration of ablation as well as the decision to interrupt RF power delivery at any time during ablation SHOULD be guided by:
  - Clinical Investigator judgment and the monitoring of ablation effectiveness parameters commonly used such as EGM reduction and/or impedance changes.

### Precautions while ablating on the Posterior wall and Coronary Sinus:

- LA posterior wall and close to the esophagus:
  - Start ablation using standard workflow for posterior wall.
  - Move/drag the catheter to a new location if clinically effective ablation is achieved within 20 seconds (EGM reduction and/or impedance drop).
  - Maximum power used SHOULD NOT exceed 35 W.
  - Duration of ablation as well as the decision to interrupt RF power delivery at any time during ablation SHOULD be guided by:
    - Clinical Investigator judgment and monitoring of ablation effectiveness parameters commonly used such as EGM reduction and/or impedance changes
    - Esophageal temperature changes should be monitored by an endo-luminal esophageal probe or method used to move esophagus as needed (refer to)
    - Duration of ablation should not exceed 30 seconds on posterior wall.
- Ablation within the Coronary Sinus (CS):
  - A maximum of 35 W will be used if ablation is required in the CS
  - $\circ$  Duration of ablation is limited to 20 seconds per ablation location in the CS

# **29.0** APPENDIX C: JUSTIFICATION OF SAFETY PERFORMANCE GOAL

In a recent BWI study (Heliostar), the FDA had recommended using a meta-analysis for combining safety rates from relevant studies for deriving a performance goal. For this recent study, the agency had agreed to setting the performance goal by allowing a 50% increase in risk from the upper bound of the 95% confidence interval for the combined safety rate.

Data from recent clinical trials for devices similar to the device in the current study were reviewed as a first step to deriving the performance goal for the safety endpoint. The following trials were reviewed: TOCCASTAR, ZERO-AF, and SMART-AF. A meta-analysis approach was taken to estimate the average composite endpoint rate. Since the definition of the safety composite varies across the studies reviewed, individual complication rates were reviewed and utilized to derive composite rates from each trial that are more closely aligned with the proposed endpoint definition. Table 1 summarizes the event rates as observed in each of the trials.

	TactiCath TM CF (n=152)	TactiCath TM TC (n=143)	Zero AF Blazer Open- Irrigated (n=157)	Zero AF Thermocool (n=164)	Smart AF (n=161)
Design	R	CT .	R	СТ	Single
Device /Procedure Death					
Atrial esophageal fistula					
Myocardial Infarction			1 (0.6%)	0 (0.0%)	
Cardiac tamponade/Perforation	1 (0.66%)	1 (0.70%)	4 (2.5%)	3 (1.8%)	4(2.5%)
Thromboembolism			1 (0.6%)	0 (0.0%)	
Stroke/CVA					
TIA					
Phrenic nerve paralysis					
PV Stenosis	0 (0.0%)	1 (0.7%)	1 (0.6%)	2(1.2%)	
Major Vascular Access/ Bleeding Complication			2(1.3%)	2(1.2%)	3 (1.86%)
Pulmonary or bronchial complication			5 (3.2%)	4 (2.4%)	
Pericarditis	2(1.3%)	0 (0.0%)	1 (0.6%)	0(0.0%)	2(1.24%)
Hospitalization					6(3.72%)
Heart Block					1 (0.62%)
Pericardial Effusion					1 (0.62%)
AF or AFL requiring cardioversion (12M)					
Atrial arrhythmia			1 (0.6%)	1 (0.6%)	
All cause death			1 (0.6%)	1 (0.6%)	
Events*					17
Subject level rate	3 (1.97%)	2(1.4%)	16(10.2%)	13 (7.9%)	16 (9.9%)

#### Table 1: Observed event rates

\* Number of events observed if reported.

Table 2 summarizes the event rates consistent with the proposed safety composite definition.

 Table 2: Observed event rates consistent with the proposed safety composite definition (Translated safety rates)

	TactiCath ™ CF (n=152)	TactiCath™ TC (n=143)	Zero AF Blazer Open- Irrigated (n=157)	Zero AF Thermocool (n=164)	Smart AF (n=161)
Design	R	CT	R	CT	Single
Device / Procedure Death					
Atrial esophageal fistula					
Myocardial Infarction			1 (0.6%)		
Cardiac tamponade/ Perforation	2(1.3%)	2(1.4%)	4(2.5%)	3 (1.8%)	4(2.5%)
Thromboembolism			1 (0.6%)		
Stroke/CVA					
TIA					
Phrenic nerve paralysis					
PV Stenosis		1 (0.7%)	1 (0.6%)	2(1.2%)	
Major Vascular Access/Bleeding Complication	3 (2.0%)	3 (2.1%)	2 (1.3%) 1 Hematoma (Ablation procedure) 1 Sanguineous drainage	2 (1.2%) 1 AV fistula 1 Rectus Sheath Hematoma	3 (1.86%)
Pulmonary or bronchial complication	2(1.3) P. edema	2 (1.4%) P. edema	5 (3.2%) 2 Heart failure / pulmonary edema 3 Pulmonary	4 (2.4%) Pulmonary	
Pericarditis	2(1.3%)		1 (0.6%)		3 (1.86%)
Heart Block					1 (0.62%)
Event total	9 (5.9%)	8(5.6%)	14 (8.9%)	11 (6.7%)	11 (6.8%)
Rate *	7 (4.6%)	8(5.6%)			11 (6.8%)

\*Number of subjects with events if reported.

# Figure 1 Meta-analysis results

	Patients w					Weight	Weight
Study	Events	Total		Proportion	95%-CI	(fixed)	(random)
TactiCath CF	7	152 —		0.05	[0.02; 0.09]	14.1%	14.1%
TactiCath TC	8	143 ·		0.06	[0.02; 0.11]	15.9%	15.9%
Smart AF	11	161		0.07	[0.03; 0.12]	21.6%	21.6%
Zero-AF TC	11	164		0.07	[0.03; 0.12]	21.6%	21.6%
Zero-AF Blazer	14	157	-	0.09	[0.05; 0.15]	26.8%	26.8%
Fixed effect mo Random effects Heterogeneity: $I^2$ =	model	777			[0.05; 0.09] [0.05; 0.09]	100.0% 	 100.0%
notorogeneity. I	0.0, 0 = 0, p =		2 0.04 0.06 0.08 0.1 0.12 0.14	4			

Figure 1 shows the result of the meta-analysis for combining the safety rates. Based on the plot, the upper bound of the 95% confidence interval was estimated to be equal to 9%. The proposed performance goal of 14% would reflect an approximately 50% increase in risk from the upper bound of the 95% CI.

# **30.0 APPENDIX D ADAPTIVE DESIGN MAIN STUDY**

# Simulation Report for Q-FFICIENCY Study Main Study

### **30.1** Introduction

This document describes the single-arm trial design for Biosense Webster's pre-market clinical evaluation of the QDOT MICROTM Catheter to demonstrate the acute safety and 12-months effectiveness. The trial will enroll N=185 subjects. One interim analysis for early success will be performed at 6 months after the last patient is enrolled.

### 30.1.1 Endpoints

### 30.1.1.1 Primary Efficacy Endpoint

The primary effectiveness endpoint is freedom from documented atrial arrhythmia (atrial fibrillation (AF), atrial tachycardia (AT) or atrial flutter (AFL)) episodes at Month 12 (that is, during the 9-month post-blanking period). The proportion of patients that are free from failure at Month 12 will be compared against a performance goal (PG) of 50%.

### 30.1.1.2 Primary Safety Endpoint

The primary safety endpoint is occurrence of primary adverse events(PAE) within 7 days of an ablation procedure. The PAE rate will be compared against a PG of 14%. PAE includes the following AEs and are defined in the protocol:

- Death
- Atrio-Esophageal Fistula
- Cardiac Tamponade/Perforation
- Myocardial Infarction
- Stroke / Cerebrovascular Accident
- Thromboembolism
- Transient Ischemic Attack
- Diaphragmatic Paralysis
- Pulmonary Vein Stenosis
- Pericarditis
- Vagal Nerve Injury
- Major Vascular Access Complication / Bleeding

### 30.2 Adaptive Design

### **30.2.1** Primary Analysis

The primary goal of the trial is to demonstrate effectiveness and safety. For the trial to be successful, both primary safety and effectiveness endpoints must be statistically significant relative to their respective PGs.

The effectiveness endpoint will be assessed by testing the hypotheses (assuming early success for effectiveness is not achieved):

	Biosense Webster, Inc	
Version 5.0 – Feb 3, 2021	CONFIDENTIAL	Page 127 of 135

$$H_0: p_E \le 0.50$$
 vs.  $H_A: p_E > 0.50$ ,

where  $p_E$  is the proportion of patients free from effectiveness events.

Let X be the number of patients that are failure-free through 12 months. We model the number of patients free from an event as

$$X \sim \text{Binomial}(n, p_E),$$

where *n* is the number of patients. We use a vague Beta(1, 1) prior distribution for  $p_E$ . Then the posterior distribution is

$$(p_E|x,n) \sim \text{Beta}(1+x,1+n-x).$$

Similarly, the hypothesis test for the safety endpoint is:

$$H_0: p_S \ge 0.14$$
 vs.  $H_A: p_S < 0.14$ ,

where  $p_S$  is the 7-day PAE. We model the number of patients with PAEs as

$$Y \sim \text{Binomial}(n, p_S)$$

with a vague Beta(1, 1) prior distribution on  $p_s$ .

Assuming early success for effectiveness is not achieved, the trial will be considered a success if BOTH

- 1.  $\Pr(p_E > 0.5 | x, n) > 0.9775$  AND
- 2.  $\Pr(p_S < 0.14 | y, n) > 0.975.$

These thresholds control the overall Type I error rate for the trial below one-sided 2.5% (see Section 29.5.1 of this report for additional discussion of Type I error control).

### **30.2.2** Interim Analyses for Early Success

One interim analysis is planned for an early success claim. The interim will occur 6 months after enrollment is complete; that is, 6 months before the final analysis. For the safety endpoint, the outcome for all patients will be known at the time of the interim analysis and therefore the primary safety analysis will be performed at the time of the interim analysis. It should be noted that because these two tests are identical there will not be an increase in type-I error.

At the interim analysis, the trial will declare early success if:

1. The safety objective is met.

Biosense Webster, IncVersion 5.0 – Feb 3, 2021CONFIDENTIAL

2. Posterior probability of the effectiveness proportion  $p_E$  being greater than 50% is greater than 0.9975.

3. .

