1	7. Severe mitral regurgitation (Regurgitant volume $\geq 60$ mL/beat, Regurgitant fraction $\geq 50\%$ , and/or Effective regurgitant orifice area $\geq 0.40$ cm  )
1:	8. Awaiting cardiac transplantation or other major cardiac surgery within the next 12 months (365 days)
1	9. Unstable angina
2	0. active systemic infection or sepsis
2	1. Diagnosed atrial myxoma or presence of an interatrial baffle or patch.
2.	2. Presence of implanted ICD/CRT-D.
2.	3. Significant pulmonary disease, (e.g., restrictive pulmonary disease, constrictive or chronic obstructive pulmonary disease) or any other disease or malfunction of the lungs or respiratory system that produces chronic symptoms.
2.	4. Severe Gastroesophageal Reflux Disease (GERD; active requiring significant intervention not including OTC medication)
2.	5. Significant congenital anomaly or medical problem that in the opinion of the investigator would preclude enrollment in this study.
2	6. Women who are pregnant (as evidenced by pregnancy test if pre- menopausal), lactating, or who are of child bearing age and plan on becoming pregnant during the course of the study
2	7. Enrollment in an investigational study evaluating another device, biologic, or drug.
2	8. Presence of intramural thrombus, tumor or other abnormality that precludes vascular access, or manipulation of the catheter.

[figure not shown]
	29. Presence of an inferior vena cava filter.
	30. Presenting contra-indication for the devices (e.g. TTE, CT, etc.) used in the study, as indicated in the respective instructions for use.
	31. Life expectancy less than 12 months
	For the Main study:
	Primary Safety Endpoint
	Sample Size and Power Calculations
	• Based on a performance goal of 14%, an anticipated rate of 7% for the primary safety endpoint, approximately 185 evaluable subjects will provide at least 80% power to declare success for the primary safety endpoint in the main study controlling one-sided alpha of 2.5%, assuming a 5% attrition rate.
	Primary Effectiveness Endpoint
	Sample Size and Power Calculations
	• Based on a performance goal of 50%, and anticipated freedom from AF/AT/AFL recurrence rate of 65%, approximately 185 evaluable subjects will be required to obtain at least 80% power to declare success for primary effectiveness endpoint in the main study controlling one-sided alpha of 2.5%, assuming a 12% attrition rate.

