### 8.2 Study Endpoints

### 8.2.1 Primary Safety Endpoint

The primary safety endpoint is the incidence of any primary adverse event occurring within 7 days of the AF ablation procedure (including the initial and repeat procedures), using the QDOT MICROTM catheter per protocol, except atrio-esophageal fistula and PV stenosis, which may also be considered as primary adverse events if occurring greater than seven (7) days and up to 90 days post the ablation procedure.[55, 56]

Primary adverse events include the following conditions (refer to Table 14.2.1A: Primary Adverse Events for detailed instructions for defining these adverse events):

- Death
- Atrio-esophageal fistula
- Cardiac Tamponade\*+/Perforation+
- Myocardial infarction (MI)
- Stroke / Cerebrovascular accident (CVA) †, ††
- Thromboembolism
- Transient Ischemic Attack

- Phrenic Nerve Injury/Diaphragmatic paralysis
- Heart block
- PV stenosis
- Pulmonary edema (Respiratory Insufficiency)
- Vagal Nerve Injury
- Pericarditis
- Major vascular access complication / bleeding
- \* Hemodynamic compromise or instability is defined as Systolic BP < 80 mm Hg.
- + Cardiac Tamponade/Perforation occurring within 30 days of the AF ablation process will be considered Primary AEs
- † Subjects with non-focal global encephalopathy will not be reported as a stroke without unequivocal evidence based upon neuroimaging studies.
- †† Modified Rankin score assessments should be made by certified individuals.

Data from recent clinical trials for devices similar to the device in the current study were reviewed as a first step to deriving the performance goal for the safety endpoint. A metaanalysis approach was taken to estimate the average composite endpoint rate. Figure 8.2.1 presents the results of the meta-analysis for combining the safety rates. Based on the plot, the upper bound of the 95% confidence interval was estimated to be equal to 9%. The proposed performance goal of 14% would reflect an approximately 50% increase in risk from the upper bound of the 95% CI. Details of the meta-analysis can be found in Appendix C.

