## **13.8** Standard Tests and Procedures

The required schedule for subject treatments and evaluations is summarized in Table 13.8A.

	Scree Base	• /			e Call		phor	ne visit)	alth or	
			Study Abl  Day 0	D/C	7 D D7-10	1 M D23- 37	3 M D76- 104	6M D150- 210	12M D335- 395	U NS
Visit no.	1	2	3	4	5	6	7	8	9	10
Informed consent 	Х									
Inc & Excl Criteria	Х									
Demographics	Х									
Vital Signs	Х									
Physical Exam		$X^{17}$		$X^{17}$		Х	Х	X 	Х	Х
NIHSS		Х		Х						
Med History 	Х				X 	X 	X 	X 	$X^2$	X 
Arrhythmias History	X									
ECG		Х		Х		Х	Х	Х	Х	Х
Adverse Events 		Х	Х	Х	Х	Х	Х	Х	Х	Х
CHA2DS2-Vasc Score	X									
NYHA Scale		Х								
QOL Assessment 		Х					Х	Х	Х	
Preg Test 		Х								
LA thrombus Imaging 			X 							
TTE 		X 		X9						
Concomitant Medications 		Х	Х	Х	Х	Х	Х	Х	Х	Х
mRS 					X 	$X^{16}$	$X^{16}$	X 	$X^{16}$	X 
PV CT/MRA Subset 	Х						X 			
PV Stenosis CT/MRA 					X 	X 	X 	X 	X 	X 
Ablation Assessments			Х							
Repeat Ablation 						Х	Х	Х	Х	Х
Device Deficiency			Х							
Health Economic Data Collection 				X 	X 	X 	X 	X 	X 	X 
AF/AT/AFL recurrence				Х	Х	Х	Х	Х	Х	Х
TTM 							Х	Х	Х	Х

Table 13.8A: Schedule of Treatments and Evaluations

Biosense Webster, Inc CONFIDENTIAL

	Pre- Proced.				Phon e Call	(via	in-clini	-Up Visit c, telehe ne visit)		
		ning / eline	Study Abl  Day 0	D/C	7 D D7-10	1 M D23- 37	3 M D76- 104	6M D150- 210	12M D335- 395	U NS
Visit no.	1	2	3	4	5	6	7	8	9	10
24-hour Holter									Х	
Subject Completion/ discontinuation form 									X 	

-  Initial ablation procedure should be done within 30 days of consent.
-  Collected to confirm no changes in medical history since last visit
-  AEs collected once consent has been signed Collected to confirm no changes in medical history since last visit.
-  If AE results in hospitalization, health economic data collection is required.
-  Quality of life tools (AFEQT).

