# **18.4.1 Primary Endpoint(s) and Associated Hypotheses**

Acute Safety: The primary safety endpoint is the proportion of subjects with any Primary Adverse Event occurring within 7 days of ablation procedure. The PAE rate will be compared against an PG of 14%.

The primary safety endpoint will be assessed by testing the hypotheses:

 $H_0: p_s \ge 0.14$  vs.  $H_A: p_s < 0.14$ ,

where  $p_s$  is the proportion of patients with PAE at early onset (within 7 days of ablation procedure).

The primary safety analysis will be performed at the time of the interim analysis for the Main study. In the variable flow study, the primary endpoints will be evaluated after full 12-month follow-up is completed on all subjects.

**12-Month Chronic Effectiveness**: The primary effectiveness endpoint is the proportion of patients that are free from documented atrial arrhythmia (atrial fibrillation (AF), atrial tachycardia (AT), or atrial flutter (AFL)) episodes at Month 12 (that is, during the 9-month post-blanking period, i.e. Day 91-365).

The primary effectiveness endpoint will be assessed by testing the hypotheses:

 $H_0: p_E \le 0.50$  vs.  $H_A: p_E > 0.50$ ,

where  $p_E$  is the proportion of patients that are free from AF, AT, and AFL episodes at 12month follow-up (includes a 3-month blanking period).

In case early success is achieved, the study will continue to follow up the subjects for the full follow-up duration. The primary effectiveness endpoints based on full 12-month follow-up data will be descriptively summarized in subjects in the PP population. The primary effectiveness endpoint in the variable flow study will be evaluated at the end of the study, i.e. completion of 12-month follow-up in all subjects.

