#### 18.5 Levels of Significance

The type I error for the interim and final analyses of the primary endpoints for the main study is controlled at one-sided 2.5%. Two-sided 95% confidence intervals will be presented around the percentages unless otherwise specified. For the variable flow study, both primary endpoints will be tested at the end of the study at the 2.5% significance level, and all confidence intervals will be presented at the 95% confidence level unless otherwise specified.

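### The Main study's safety test assumes that every safety outcome is known 6 months after last enrolment, but the endpoint definition and the consent-based clock do not guarantee it

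*Protocol*

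**What the plan says.** **Timing.** Protocol Appendix D, section 30.1: "One interim analysis for early success will be performed at 6 months after the last patient is enrolled". Section 30.2.2 adds: "For the safety endpoint, the outcome for all patients will be known at the time of the interim analysis", and places the primary safety analysis there for that reason. Sections 18.4.1, 18.9.4 and 18.9.6 agree, and under 18.9.4 a study that does not meet the safety endpoint is unsuccessful.

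**Endpoint.** Section 8.2.1 counts PAEs "within 7 days of the AF ablation procedure (including the initial and repeat procedures", where the study catheter was used per protocol. Tamponade or perforation counts to 30 days, and atrio-esophageal fistula and PV stenosis to 90 days. No latest date is set for a qualifying repeat.

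**Clock.** Section 8.1 treats a subject as enrolled on signing consent. Table 13.8A, note 1: "Initial ablation procedure should be done within 30 days of consent".

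**Repeats.** Study-catheter repeats are described only for the blanking period, Day 0-90 (8.2.2; Table 13.8A note 18; 13.11 note). Section 13.6 says that repeats in follow-up may use an approved catheter. Section 13.11 leaves repeats to the physician's discretion and sets no end date.

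**Completeness rule.** Section 18.9.7 excludes an event-free subject from the interim safety analysis only if the 3-month follow-up is missing.

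**Variable Flow.** Section 18.4.1: "In the variable flow study, the primary endpoints will be evaluated after full 12-month follow-up is completed on all subjects".

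**The concern.** The Main safety verdict can decide the trial, and its timing rests on one factual premise: that no subject can still acquire a PAE. The endpoint follows every qualifying procedure, while the calendar runs from consent and the visit schedule from the index ablation. A subject re-ablated with the study catheter on Day 85 who attends the 3-month visit is analysed as event-free while the 90-day window for fistula and stenosis is still open.

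The error has one direction. A PAE that occurs after the cut is never counted, so incomplete windows can only make it easier to pass against the 14% goal. The operating characteristics do not test this, because section 30.3.2 simulates one 7-day PAE outcome per subject and models no repeat procedures.

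**Working it through.** **1. Reproduce the plan's safety figures.**

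Inputs:
- "The trial will enroll N=185 subjects" (30.1).
- "Based on a performance goal of 14%, an anticipated rate of 7% for the primary safety endpoint" (section 4.0).
- "The type I error for the interim and final analyses of the primary endpoints for the main study is controlled at one-sided 2.5" per cent (18.5).
- Beta(1,1) prior, with success if Pr(p_S < 0.14) > 0.975 (18.9.4, 30.2.1).
- Safety dropout of 5% per year (30.3.4), applied here up to the 3-month completeness point: 185 × 0.95^0.25 = 182.6, so n = 183.

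The posterior is Beta(1+y, 1+n−y). At n = 183, 16 subjects with a PAE give posterior probability 0.980 (pass) and 17 give 0.966 (fail).

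- Power: P(Y ≤ 16 | 183, 0.07) = 0.857, against 0.860 in Table 5.
- Joint power: 0.857 × 0.952 (Table 5 effectiveness) = 0.816, against 0.817.
- Type I error: P(Y ≤ 16 | 183, 0.14) = 0.021, against 0.021 in Table 5 and a largest value of 0.023 in Table 4.

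The stated figures are right on their own inputs.

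**2. Narrow reading: study-catheter repeats only to Day 90.**

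- Latest 7-day window: 90 + 7 = Day 97. Latest 30-day window: 90 + 30 = Day 120. Latest 90-day window: 90 + 90 = Day 180.
- Last subject at the interim, using the 30-day month of section 13.7: 6 × 30 − 30 = Day 150 if ablation came 30 days after consent, or Day 180 if it came the same day.
- At Day 150 all 7-day and 30-day windows are closed. A 90-day window is open only for a repeat after 150 − 90 = Day 60.
- This affects subjects from the last enrolment month: 30 of 185 expected, 35 fast, 18 slow (Table 3 of Appendix D).

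The documents give no repeat rate. Assume that 15% of those 30 have such a repeat. Section 6.4.1 puts severe PV stenosis below 1% and fistula at about 0.1%: 30 × 0.15 × 0.011 = 0.05 events. With the 5% planning rate for moderate or severe stenosis in 8.1.1: 30 × 0.15 × 0.051 = 0.23. Both overstate the gap, because they count the whole 90-day window although at most its last 30 days are open.

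**3. Literal reading: study-catheter repeats count at any time.**

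With expected enrolment of 5, 15, 25, 30, 40, 40 and 30 per month, the interim falls at month 7 + 6 = 13. Taking month midpoints and treating enrolment as ablation, only the first 5 subjects have passed 12 months, so 180 of 185 are still in follow-up (185 fast, 173 slow).

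Follow-up still to come: 15×0.5 + 25×1.5 + 30×2.5 + 40×3.5 + 40×4.5 + 30×5.5 = 605 person-months. As a share of Day 91-365 follow-up: 605 / (185 × 9) = 0.363 (0.40 fast, 0.31 slow).

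Assume that 5-15% of subjects have a study-catheter repeat after Day 90, spread evenly, with 7% PAE risk per repeat, each in a subject with no earlier PAE:

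- Low: 185 × 0.05 × 0.363 × 0.07 = 0.24 missed PAEs.
- High: 185 × 0.15 × 0.363 × 0.07 = 0.71 missed PAEs.

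If the true rate over the full endpoint is 14%, the rate seen at the cut is 0.14 − missed/183:

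- Low: 0.14 − 0.24/183 = 0.1387, and P(Y ≤ 16) = 0.024.
- High: 0.14 − 0.71/183 = 0.1361, and P(Y ≤ 16) = 0.030.

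The 0.025 line is crossed at about one third of a missed event.

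**The case against.** The strongest reply is that the premise is nearly true by design. Only study-catheter procedures count, and every description of a study-catheter repeat is confined to the blanking period. The catheter is investigational, and 13.6 points to an approved one in follow-up. On that reading 90 + 90 = 180 days, which is the interim date. This largely stands, but 13.6 neither names nor excludes the study catheter, and 8.2.1 has no cut-off.

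Second, 30.2.2 also places the interim 6 months before the final analysis, and 18.1 speaks of 185 evaluable subjects, who by 9.5 have been ablated. Both suggest a clock that starts at the last ablation. That is a possible reading, but 30.1 and 30.2.2 state the anchor as enrolment, which the protocol defines as consent.

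Third, the test may not be the only one. Section 18.7 places final safety and effectiveness analyses after 12 months if there is no early success, 30.2.2 refers to two identical tests, and 18.9.8 runs safety sensitivity analyses at 12 months. The supplied SAP covers Variable Flow only. This is fair: the text is ambiguous and needs reconciling.

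Fourth, late repeats may not be evenly spread. Section 30.3.1 uses a failure hazard that is much higher early. If repeats followed it, about 12% rather than 36% would remain, giving 185 × (0.05 to 0.15) × 0.12 × 0.07 = 0.08-0.23 missed PAEs, which stays under 0.025. This is approximate, since repeats lag recurrence.

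A reader might also infer that Main data borrowed into Variable Flow cover a shorter PAE period. The documents do not show that. Nothing in SAP 7.4 to 7.6 freezes Main safety data at the interim. Variable Flow enrols only after Main enrolment is complete and is tested after its own 12-month follow-up, by when Main subjects should have completed theirs.

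**Conclusion.** The claim that every safety outcome will be known is not guaranteed on either reading.

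- **Repeats to Day 90 only:** the gap is confined to the 90-day window, for repeats after about Day 60 in the last enrolment month. It amounts to well under one expected event (0.05 to 0.23 on the assumptions shown).
- **Repeats at any time:** about 180 of 185 subjects could still have a qualifying procedure. On assumed late-repeat rates of 5-15% with 7% risk each, about 0.2-0.7 PAEs are missed and the safety type I error goes from about 0.021 to 0.024-0.030. The 0.025 limit is exceeded only in the upper part of that range.

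A reader might infer that most subjects will in fact have uncounted PAE windows, or that the stated 2.5% control is broken. The documents do not support either: they describe no study-catheter repeat after Day 90 and give no rate for one. The established defect is an undefined endpoint boundary combined with an interim clock that starts at consent. It is worth correcting because the test can decide the trial and any error favours passing.

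**What to change.** - In 8.2.1, 14.2.1 and 18.4.1, define the primary safety endpoint in both studies as PAEs after the index ablation and after study-catheter repeats performed through Day 90, each with its existing window.
- In 18.9.6 and 30.2.2, set the Main safety data cut at no earlier than 180 days after the last index ablation.
- Reconcile 8.2.1, 13.6, 18.7, 18.9.7 and 30.2.2 on which repeats count, when safety is tested, and what makes a subject complete. Table 14.2.1A, which describes related death at any time, should be aligned with the 7-day rule in the same pass.
- Report PAEs after any later study-catheter repeat separately at 12 months.
- State in the Variable Flow SAP that the borrowed Main safety data use the same window.

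If the sponsor prefers to keep all repeats in the endpoint, the safety claim should rest on complete 12-month data. That costs more, because 18.9.6 makes early success conditional on safety already being met.

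The preferred change costs protocol and SAP wording, moves the interim by up to about one month, and shifts any late-repeat PAEs from the primary endpoint to a separate table.
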